Protection against risk.....	32
Data protection.....	33
Potential benefits of the study to participants and society.....	33
Dissemination	33
Trial governance.....	33
Abbreviations	34
Competing interests.....	35
Trial Steering Committee	35
References.....	36

Overview

Title	GeneXpert Performance Evaluation for Linkage to Tuberculosis Care: The XPEL TB Trial
Target Population	Adults undergoing evaluation for pulmonary TB (N=11,283)
Sites	20 TB microscopy centers (10 intervention, 10 control) in Uganda
Study Design	Clustered-randomized trial with nested mixed methods and economic/transmission modeling studies
Study Duration	18 months
Objectives	
Aim 1: To compare patient outcomes at health centers randomized to intervention vs. standard-of-care TB diagnostic evaluation strategies.
 
 • Intervention: onsite molecular testing for TB + process redesign to facilitate same-day TB diagnosis and treatment + performance feedback • Standard-of-care: onsite ZN or LED fluorescence microscopy + hub-based GeneXpert testing per existing protocols 
Aim 2: To identify processes and contextual factors that influence the effectiveness and fidelity of the intervention TB diagnostic evaluation strategy.
 
Aim 3: To compare the costs and epidemiological impact of intervention vs. standard-of-care TB diagnostic evaluation strategies.

Key Roles

Principal Investigator

[name], MAS
Associate Professor of Medicine, University of California San Francisco
San Francisco General Hospital
[name]
[name]
[contact]
[contact]
[contact]

Uganda Principal Investigator

[name], MSc, PhD
Senior Lecturer, Makerere University College of Health Sciences
[name]
Kampala, Uganda
[contact]
[contact]
[contact]

NHLBI Program Officer

[name]
AIDS Program Lung Team Leader
[contact]

Table 1. Timeline of Activities

	2018				2019				2020				2021			
	Q1	Q2	Q3	Q4												
Randomization and site training																
Randomization unveiling ceremony																
Post randomization site visits (to introduce intervention or conduct guideline refresher training)																
Assess patient-level outcomes																
Collect TB diagnosis and treatment initiation data																
Collect 6-month vital status data																
Assess intervention implementation (intervention sites)																
Collect process metric data																

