c) Health facility environment	c) Sum of score on 2 question items (Q4 and 5)
d) Provider interpersonal skills	d) Sum of score on 5 question items (Q7-11)
e) Provider technical competence	e) Sum of score on 4 question items (Q12-15)
Provider survey:	
a) Intention	a) Score on 1 question item (Q4)
b) Attitudes/beliefs	b) Sum of score on 3 question items (Q5a, 6a, and 6b)
c) Social norms/expectations	c) Sum of score on 2 question items (Q5b, 6c and 6d)
d) Self-efficacy/behavioral control	d) Sum of score on 5 question items (Q5c, 6e and 6f)

Intervention arm only		
Outcome	Numerator	Denominator
Process metrics:		
a) GeneXpert device non-operation days	a) GeneXpert device non-operation days ¹	a) Total number of lab operation days ¹
b) Proportion tested by GeneXpert:	b) Number with GeneXpert result date	b) Number tested by GeneXpert ²
1. On same day as initial sputum submission	1. Same as initial sputum submission date ²	
2. By next day after initial sputum submission	2. By next day after initial sputum submission date ²	
c) Proportion with indeterminate results	c) Number with coded error, invalid or no test result ²	c) Number of initial GeneXpert tests done ²
d) Proportion with coded error result	d) Number with coded error result ²	d) Number of initial GeneXpert tests done ²
e) Proportion with invalid result	e) Number with invalid result ²	e) Number of initial GeneXpert tests done ²
f) Proportion with “no test” result	f) Number with “no test” result ²	f) Number of initial GeneXpert tests done ²
g) Proportion with GeneXpert test repeated if initial result indeterminate	g) Number with second GeneXpert result ²	g) Number with initial indeterminate GeneXpert result ²
	h) # treated on same day as initial health center visit ³	h) # Xpert-positive ²

h) Proportion treated on same-day if Xpert-positive	i) Number of Report Cards with Comments section filled ⁴	i) Total number of report cards issued to health centers ³
i) Proportion of report cards reviewed at staff meetings	Variation in and barriers to intervention strategy uptake	Themes emerging from focus group discussions, semi-structured interviews with health center staff

Source of data: ¹ Health center laboratory log; ² GeneXpert Software; ³ Treatment register; ⁴ Performance feedback report card

IV. Cost-effectiveness/Modeling Outcomes

Outcome	Definition	Source

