1) Descriptive analyses – We will report process metrics on a monthly basis to assess adoption and maintenance of each intervention component overall, within key patient sub-groups, and at individual sites. We will report median and change between pre- and post-randomization assessments in **A) patient costs**; **B) patient satisfaction with care**; and **C) provider TPB construct scores** at control and intervention sites.

2) Comparative analyses – To identify patient-, provider-, and/or clinic-level factors independently associated with adoption and maintenance of intervention components, we will develop linear or logistic regression models, taking into account the clustered design (for example, robust standard errors). To compare by study arm the change from baseline (pre-randomization) to post-intervention in **A) patient cost**; **B) patient satisfaction with care**; and **C) TPB construct scores**, we will use a cluster-level analysis, similar to methods described for the primary outcome under Aim 1. The analysis will take into account the stratified design and an adjusted analysis will also be conducted taking into account other baseline imbalances by study arm.

3) Qualitative analyses – De-identified focus group or interview transcripts will be uploaded to the qualitative data analysis software Dedoose (SocioCultural Research Consultants, USA). Thematic interpretation³²⁻³⁴ will include collaborative development of a coding framework and detailed coding of transcripts using Dedoose. Coded transcripts will be sorted to identify thematic groupings. The thematic groupings will be reviewed to identify emergent themes within each domain of the coding framework and quotes that best represent each domain. Thematic interpretation will focus on individual, social and structural factors associated with successful or unsuccessful adoption and/or maintenance of the intervention components at different sites.

Aim 3

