Original detectable effect size estimates: The study is based on the health clinic being the unit of randomization and aims to demonstrate the superiority of the intervention arm. The sample size calculation uses formulae appropriate for cluster-randomized trials with a parallel design and stratified and/or restricted randomization, including the addition of one extra cluster per arm to allow for the loss of degrees of freedom due to stratification to obtain conservative estimates.²⁶ The original detectable effect size estimates were based on the outcome being the proportion of patients treated for microbiologically-confirmed TB within two weeks of referral for sputum-based testing. A type I error of 5% and power of 90% was assumed. Pre-randomization data collected from January to December 2017 from the 20 selected trial sites in Uganda suggests the average proportion of patients referred for TB evaluation who initiate treatment for active TB within two weeks is 6.7%, and the coefficient of variation (k) between clusters is 0.36, with a harmonic mean of 268 patients enrolled at each health center cluster during the 18-month enrolment period. Based on these assumptions and assuming a type I error of 5%, we will have 90% power to detect a 6% or greater absolute increase in the outcome proportion in the intervention arm with a trial duration of 18 months (see **Table**). Table 1 also shows detectable absolute effect sizes with varying power (80%, 85%, 90%) during various trial time intervals and respective average cluster size estimates.

Average cluster size	Effect size (10 clusters per arm, $k=0.36$)		
	80% Power	85% Power	90% Power
178 (12 months)	5.9%	6.5%	7.4%
223 (15 months)	5.7%	6.3%	7.1%
268 (18 months)	5.5%	6.1%	6.9%
312 (21 months)	5.4%	6.0%	6.7%
357 (24 months)	5.3%	5.9%	6.6%

Revised detectable effect size estimates: The revised detectable effect size estimates are for the outcome being the number of patients treated for microbiologically-confirmed TB within two weeks of referral for sputum-based testing. We first used 10 months of pre-intervention period data across all 20 clinics to assess 1) the geometric mean number of patients diagnosed and treated

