for TB within 14 days (new primary outcome), the natural log (ln) of the geometric mean and 3) the standard deviation of the natural log at control sites, intervention sites and overall.. For the pre-intervention period, the intervention clinics have a lower geometric mean number of clinic attendees who were diagnosed with TB and started on TB treatment within 14 days compared with the control arm:

	Geometric mean	Mean of ln outcome	SD of ln outcome
Control	14.70	2.69	0.23
Intervention	6.49	1.87	0.32

We then estimated the detectable effect size (expressed as a geometric mean ratio). The calculations assume the same parameters as for the original primary outcome (10 clinics/arm, 18-month trial duration to achieve geometric mean of 286 patients/cluster in control and intervention arms). Table 1 below shows the detectable effect size assuming within-arm SD of ln outcome of 0.2 to 0.3 and power of 80-90%. The detectable effect sizes shown below are conservative (calculations do not take into account the baseline differences between arms in the new primary outcome and are based on 10-months rather than full 24-months of pre-intervention data). Final calculations will be repeated once baseline data is fully entered and available for analysis.

Table 3: Detectable effect sizes

SD of ln outcome	Geometric Mean Ratio of the new primary outcome (intervention vs control)	
	80% power	90% power
0.2	1.30	1.36
0.3	1.49	1.58

We believe a GMR of 1.30-1.58 is a reasonable detectable effect size. Xpert MTB/RIF is twice as sensitive as smear microscopy (double the number of confirmed TB cases) and we expect onsite testing to reduce pre-treatment loss to follow-up by at least half (from 30% to <15%).

Aim 2

The sample size for Aim 2 analyses is either fixed (process metrics; provider surveys and focus groups) by parameters of the clinical trial or based on feasibility considerations (patient surveys and provider in depth interviews). For quantitative analyses, the sample size is sufficiently large (data on 3400 patients for process metrics analyses, 800 patient surveys, and 100-200 provider surveys) to enable multivariable analysis to identify factors associated with intervention adoption and maintenance.

Aim 3

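### Aim 2 looks for clinic-level factors behind uptake on 10 intervention clinics, naming only robust standard errors with no small-sample correction, and justifies the sample by counting individuals

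*Combined protocol and SAP*

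**What the plan says.** The amended protocol (Statistical Analysis, Aim 2, comparative analyses) sets this goal: "To identify patient-, provider-, and/or clinic-level factors independently associated with adoption and maintenance of intervention components". The method is: "we will develop linear or logistic regression models, taking into account the clustered design (for example, robust standard errors"). No reference distribution, small-sample correction or limit on covariates is given.

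The process metrics that measure adoption and maintenance are listed under "Intervention arm only" (Implementation Outcomes). The timeline agrees: "Assess intervention implementation (intervention sites"). The Overview gives "20 TB microscopy centers (10 intervention, 10 control) in Uganda", so these models have 10 clusters.

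Sample Size Considerations, Aim 2, states that "the sample size is sufficiently large (data on 3400 patients for process metrics analyses, 800 patient surveys, and 100-200 provider surveys"). The purpose that this size is said to serve is "to enable multivariable analysis to identify factors associated with intervention adoption and maintenance". The number of clinics does not appear in that paragraph.

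Safeguards for few clusters appear elsewhere. The protocol promises them for the Aim 1 arm comparison. SAP sections 4.4.1, 4.4.2 and 4.4.4.2 give cluster summaries, account for lost degrees of freedom and use t on 16 df. The Aim 2 comparison between arms of costs, satisfaction and provider scores is also cluster-level. None of these covers the factor models. The amended SAP (section 2.3 and its amendment log) is limited to effectiveness outcomes, so the protocol text is all there is.

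**The concern.** A clinic-level factor, such as distance to the Xpert hub or urban location, takes one value per clinic. More patients per clinic measure each clinic's uptake more precisely but add no clinics. The cluster sandwich variance is estimated from cluster residuals. With 10 clusters it is biased downward, and more so when several clinic-level covariates are fitted together, as a search for independent associations invites.

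Aim 2 is meant to help explain why uptake differed between sites, and SAP section 2.3 treats implementation as coprimary with clinical effectiveness. Chance differences between clinics could be reported as independent determinants of adoption.

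**Working it through.** **The plan's own figure.** The documents give no error rate, power or detectable effect for these models, so there is nothing to reproduce directly. As a check on the shared design, Table 3 (Aim 1) follows from GMR = exp[(1.960 + z_power) × SD × √(2/9)], with 9 = 10 − 1 clusters per arm. This gives 1.302, 1.357, 1.486 and 1.582, against the stated 1.30, 1.36, 1.49 and 1.58. Aim 1 therefore counts clinics, while Aim 2 counts individuals.

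**Inputs from the documents.** 10 intervention clinics; about 3400 patients. The 5% level is stated for Aim 1 only ("A type I error of 5% and power of 90% was assumed"); I assume two-sided 5% for Aim 2.

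**Assumed inputs, not given for Aim 2.** Between-clinic SD 0.2–0.8 on the logit scale (linear model: ICC 0.05); clinic sizes equal or with CV 0.5; a binary factor split 5:5, 3:7 or 2:8, or a continuous factor; one to three clinic-level covariates. A separate set of logistic runs, with logit SD 0.4–0.7 and size CV up to about 0.6, went to four covariates.

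**Method.** Data were generated with no association. The sandwich variance is V = G/(G − 1) × (X′X)⁻¹[Σ X_g′e_g e_g′X_g](X′X)⁻¹ with G = 10 (CR1), or its logistic analogue. The ratio b/√V was compared with the normal value or with t on 9 df. The comparator is ordinary regression of the 10 clinic summaries with t on 10 − 1 − p df, where p is the number of clinic-level covariates. With 6000 runs per cell, the Monte Carlo standard error at 5% is √(0.05 × 0.95/6000) = 0.28 points.

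**Type I error (%), clinic-level factor, linear model, CR1**

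| Factor | Covariates | Equal sizes, z | Equal sizes, t(9) | Unequal sizes, z | Unequal sizes, t(9) |
|---|---|---|---|---|---|
| 5:5 | 1 | 10.0 | 6.6 | 13.3 | 8.8 |
| 5:5 | 3 | 18.1 | 13.1 | 20.4 | 15.5 |
| 3:7 | 1 | 13.2 | 9.0 | 16.8 | 11.9 |
| 3:7 | 3 | 20.4 | 15.9 | 24.0 | 18.9 |
| 2:8 | 1 | 22.0 | 16.8 | 25.2 | 19.7 |
| 2:8 | 3 | 26.1 | 21.2 | 30.0 | 24.2 |
| Continuous | 1 | 17.0 | 12.4 | 18.2 | 13.7 |
| Continuous | 3 | 23.8 | 18.5 | 26.0 | 20.5 |

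- Logistic model, unequal sizes: 11.7–30.5% with z, 7.7–24.9% with t(9).
- Separate logistic runs: 30–31% with z at four covariates; 6–25% with t(9) over one to four covariates.
- Without the G/(G − 1) factor, z reference: 11.6–32.6%, about two points higher.
- Regression on 10 clinic summaries: 4.4–5.6% in every setting.
- Patient-level factor (2000 runs): 8.8% with z, 5.6% with t(9).
- Provider-level factors were not simulated.

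**What 10 clinics can show.** For a 5:5 factor with 8 df, the effect detectable with 80% power is about (2.306 + 0.889) × √(1/5 + 1/5) = 3.195 × 0.632 = 2.0 between-clinic SDs, however many patients are included.

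**The counts in the sample-size paragraph.** The surveys cover all 20 sites. At the 10 clinics with adoption data there would be 10 × 40 = 400 patient surveys and 10 × 5 to 10 × 10 = 50–100 provider surveys. The 3400 has no stated derivation: 10 × 268 = 2680, and 11,283/2 is about 5642.

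**The case against.** Robust standard errors are offered as an example; the commitment is to account for clustering. A corrected sandwich with a t reference would comply, so the plan does not fix a bad method. This stands. What remains is that the only method named fails for clinic-level factors and nothing steers the analyst away from it.

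A reader might infer that the error rate under this plan is 10–31%. The documents do not support that. The range needs a normal reference that the plan never specifies, and the upper end needs three or four clinic-level covariates, which the plan does not propose. With one balanced factor, equal clinic sizes and t on 9 df, the inflation is slight (6.6%).

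A reader might also infer that the whole Aim 2 sample is inadequate. It is not. The sample-size sentence does not single out clinic-level factors, and for patient-level factors the individual counts are relevant and the inflation modest.

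Finally, no test level is set for Aim 2, and focus groups and interviews also address variation between sites. Nothing says that regression P-values alone will direct scale-up. That limits the consequence. It does not make the sample-size statement right for clinic-level factors, and the protocol does not label these associations exploratory.

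**Conclusion.** The concern holds for clinic-level factors. The structural part rests on the documents alone: there are 10 clinics with adoption data, no small-sample method for these models, and a justification that counts individuals.

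The size, roughly 6–31% at nominal 5%, rests on the assumptions listed above. Its ends move with the reference distribution, factor split, clinic sizes and number of covariates, so it is an illustrative range and not a property of the plan. Inflation appeared in every robust-error setting tried for a clinic-level factor, and regression on clinic summaries removed it. This should be corrected, but it does not threaten the trial: the primary comparison is untouched.

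**What to change.** In Statistical Analysis, Aim 2, comparative analyses:

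- For clinic-level factors, use linear regression of the 10 clinic summaries, with t on 10 − 1 − (number of clinic-level covariates) df and at most one or two such covariates per model.
- For patient- and provider-level factors, use a small-sample-corrected sandwich (CR2 or Kauermann-Carroll) with t degrees of freedom, or clinic fixed effects.

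In Sample Size Considerations, Aim 2, keep the individual counts as the justification for patient- and provider-level factors. Add that clinic-level associations rest on 10 clinics and are exploratory.

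The cost is wording only, with no new data. Fewer clinic-level factors can be fitted and the claim becomes more modest.

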This is a pragmatic trial that will study outcomes of routine care. Thus, rather than recruiting participants, the intervention and control arms will be compared using data available in routine TB laboratory and treatment registers for consecutive patients who present to participating health centers during the two-year trial period and meet eligibility criteria (estimated N=11,283 patients).

Participants for mixed methods and health economic sub-studies

Patient Cost and Satisfaction Surveys: The patient cost and satisfaction surveys will be administered during the baseline (pre-randomization) period (N=20/site; 400 total) and in the second year after randomization (N=40/site, 800 total). Health center staff will assist with identification and recruitment of patients who are interested in participating in the surveys (from among patients providing sputum samples or receiving results). Participation will be voluntary. Research staff will then contact interested patients by phone at the end of their health center visit to review the verbal consent script, answer questions the patient may have, and administer the survey to consenting patients.

Provider Survey: The provider survey will be administered during the baseline (pre-randomization) period and in the second year after randomization. All eligible providers at each study site (N=5-10/site; 100-200 total) will be invited to participate in the survey. Participation will be voluntary and written informed consent will be obtained.

Provider Focus Group Discussions and Interviews: Focus group discussions will occur during the second year after randomization and semi-structured interviews after the trial is completed. All eligible providers at intervention sites (N=5-10/site; 50-100 total) will be invited to participate in focus group discussions. Providers (N=20-30) at low- and high-performing sites will be invited to participate in semi-structured interviews. Participation in focus group discussions and interviews will be voluntary and written informed consent will be obtained.

[figure not shown]
Intervention and Control (Wait-list) Arms

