A questionnaire adapted from the routine TB case finding guide will be administered to document TB symptoms reported at each patient’s initial visit to the health clinic. This information will be used to assess the proportion of patients referred for TB testing who were eligible for testing based on reported symptoms. Surveys will be administered by phone two weeks after the patient’s initial clinic visit to avoid influencing the primary outcome. Surveys will also be administered in-person to patients who provide a sputum sample for TB testing. In-person surveys will take place during quarterly site visits. All patients who are at least 18 years old, meet the main study inclusion criteria, and enrolled over a specified three-month period will be eligible for participation in the symptom screening activity. Due to logistical feasibility, however, it is anticipated that only patients with a documented valid phone number and patients selected for in-person interviews during quarterly site visits will be included in this activity. Study staff will prioritize clinics with a smaller proportion of patients with phone numbers available for in-person interviews.

Patient surveys

We will administer cost and satisfaction with care surveys to 20 patients at each health center (N=400 total) in the pre-randomization period and to 40 patients at each health center (N=800) at least 6 months post-randomization (April-September 2019). The two surveys will involve the same patients when feasible, but administered to different patients if a patient does not wish to complete both.

The cost survey will collect data on direct and indirect costs (time to complete visit, lost wages, etc.) of TB diagnostic evaluation. Cost data collection will be based on the Tool to Estimate Patient Costs developed by the TB Coalition for Technical Assistance, which we have already adapted and used in Uganda.

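### Aim 2 compares arms on clinic-level change from baseline without naming the baseline clinic mean as a covariate, which costs precision but causes no bias

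*Combined protocol and SAP*

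**What the plan says.** The protocol, Statistical Analysis, Aim 2, item 2 (Comparative analyses), sets the task as "To compare by study arm the change from baseline (pre-randomization) to post-intervention" in patient cost, patient satisfaction and provider TPB scores. On method it says "we will use a cluster-level analysis, similar to methods described for the primary outcome under Aim 1". It accounts for the strata and adds that "an adjusted analysis will also be conducted taking into account other baseline imbalances by study arm".

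The Patient surveys section fixes the sample: "We will administer cost and satisfaction with care surveys to 20 patients at each health center (N=400 total) in the pre-randomization period", then "40 patients at each health center (N=800) at least 6 months post-randomization (April-September 2019". The Recruitment section says respondents are drawn "from among patients providing sputum samples or receiving results". The provider survey invites all eligible staff, 5 to 10 per site, before randomisation and again afterwards.

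The current SAP, section 2.3, covers effectiveness outcomes only, so it adds no method for these Aim 2 comparisons.

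**The concern.** A change score is a regression on baseline with the slope forced to 1. That suits a baseline measured with little error that tracks the later value closely. Here each clinic's patient baseline is a mean of 20 people, with half as many respondents as the later mean. Its sampling error passes in full into the estimated arm difference. An estimated slope would down-weight the noisy baseline.

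These measures are the implementation outcomes that the protocol lists for comparison across arms, and SAP section 2.3 calls effectiveness and implementation coprimary aims. The patient survey size was set by feasibility and there are 10 clinics per arm, so precision already collected is worth keeping. Naming the model in advance also stops the choice between change score and baseline adjustment being made after the data are seen.

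**Working it through.** **Stated totals.** 20 clinics × 20 = 400 and 20 × 40 = 800 patients; 20 × (5 to 10) = 100 to 200 providers. All agree with the protocol. It gives no precision figure for Aim 2.

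**Inputs.** From the protocol: 20 and 40 patients per clinic, 5 to 10 providers, 10 clinics per arm, two strata. Assumed, because the documents give none: ICC ρ from 0.02 to 0.20, correlation c of clinic effects between rounds from 0.5 to 0.9, different patients in each round, individual SD = 1.

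**Formulas, per clinic.**
- Baseline variance Vb = ρ + (1 − ρ)/20
- Later variance Vp = ρ + (1 − ρ)/40
- Covariance C = cρ
- Change score: Vb + Vp − 2C
- Baseline-adjusted: (Vp − C²/Vb) × 16/15. The factor is 1 + 1/(16 − 1), the price of estimating the slope with 16 residual degrees of freedom.

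**Central case, ρ = 0.05, c = 0.7.**
- Vb = 0.05 + 0.0475 = 0.0975; Vp = 0.05 + 0.02375 = 0.07375; C = 0.035
- Change: 0.0975 + 0.07375 − 0.07 = 0.10125, of which the 20-patient sampling error is 0.0475, or 47%
- Adjusted: 0.07375 − 0.001225/0.0975 = 0.0612; × 16/15 = 0.0653
- Change/adjusted: 0.10125/0.0612 = 1.65, or 1.55 with the factor (standard error about 25% larger)
- Change/later data alone: 0.10125/0.07375 = 1.37
- Estimated slope C/Vb = 0.36, against the imposed 1

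| ICC | c | slope | change/later only | change/adjusted (with 16/15) |
|---|---|---|---|---|
| 0.02 | 0.5 | 0.14 | 2.10 | 2.04 |
| 0.02 | 0.8 | 0.23 | 1.83 | 1.87 |
| 0.05 | 0.8 | 0.41 | 1.24 | 1.49 |
| 0.10 | 0.8 | 0.55 | 0.88 | 1.29 |
| 0.20 | 0.8 | 0.67 | 0.64 | 1.16 |
| 0.20 | 0.9 | 0.75 | 0.45 | 1.10 |

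The first and last rows bound the assumed range; √2.04 = 1.43 and √1.10 = 1.05. A simulation of 20 clinics in two strata gave 1.87, 1.52, 1.28 and 1.14 at c = 0.8 for ICC 0.02, 0.05, 0.10 and 0.20. Over a wider range (ICC 0.01 to 0.30, c 0.5 to 1.0) the ratio runs from 1.01 to 2.30.

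**Against ignoring baseline.** The change score is worse than later data alone when Vb > 2C. At c = 0.5 that always holds. At c = 0.8 it holds when 0.65ρ < 0.05, that is ρ below about 0.077.

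**Detectable difference** (80% power, two-sided 5%, c = 0.8, change against adjusted, in SD units): 0.38 and 0.28 at ICC 0.02; 0.40 and 0.33 at 0.05; 0.44 and 0.39 at 0.10; 0.50 and 0.46 at 0.20.

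**Providers** (5 to 10 in each round, ICC 0.05 to 0.20, c = 0.8, before the 16/15 factor). If the staff differ: 1.27 to 1.71. With 5 staff at ICC 0.05, V = 0.24 and C = 0.04, so 0.40/0.2333 = 1.71. If the same staff answer, with assumed individual correlation 0.5 to 0.7: 1.13 to 1.28. With 10 staff, ICC 0.20 and individual correlation 0.7, V = 0.28 and C = 0.16 + 0.7 × 0.08 = 0.216, so 0.128/0.1134 = 1.13. Dividing by 16/15 gives 1.19 to 1.61 and 1.06 to 1.20.

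**The case against.** The strongest reply is that the protocol already allows for this. It calls the method similar to that for the primary outcome, and SAP section 4.4.3 adjusts the primary count for its baseline count. It also plans an adjusted analysis. This does not settle the matter. The protocol's own Aim 1 text names no baseline-outcome covariate. The adjusted Aim 2 analysis is for other imbalances, a word that points away from the outcome's own baseline. The SAP model is written for effectiveness outcomes.

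A second reply is that the waves may share patients, since the protocol says "The two surveys will involve the same patients when feasible, but administered to different patients if a patient does not wish to complete both". Read in place, that sentence pairs the cost survey with the satisfaction survey. Separate cross-sections remain an inference from recruitment among current attendees with no re-interview described; no sentence says so outright. Even full re-interview would leave at least 20 of the 40 later respondents new.

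A third reply stands: the ICC and correlation are assumptions, and where both are high the gain is close to nothing.

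A reader might also infer that all three outcome families rest on 20 different patients per clinic. They do not: provider scores come from 5 to 10 staff, many possibly the same people in both rounds.

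**Conclusion.** The point holds as one of efficiency. For patient outcomes the planned change score has about 1.10 to 2.04 times the variance of a baseline-adjusted analysis, and 1.55 times at ICC 0.05 and correlation 0.7. For provider scores the ratio, before the small-sample factor, is about 1.13 to 1.28 with the same respondents and 1.27 to 1.71 with different ones. All of this rests on the assumed correlations.

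Four stronger readings are tempting and not supported:
- That the comparison is biased. Under randomisation the change score is unbiased, and the primary and other effectiveness outcomes are untouched.
- That adjustment would remove the baseline noise. It reduces its weight.
- That the change score is always worse than ignoring baseline. This is so only at low ICC or low correlation; at ICC 0.10 and correlation 0.8 it has 0.88 times the variance of later data alone.
- That the loss decides whether a difference can be seen, or passes into Aim 3. No target effect or power is stated for Aim 2, and the Aim 3 text does not say that this contrast is a model input.

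**What to change.** In the protocol's Aim 2 comparative analyses, state that the arm effect on each outcome is estimated by linear regression of the clinic's post-randomisation mean on arm, stratum and the clinic's baseline mean. Inference should use t on the reduced degrees of freedom: 16 with those terms, against 17 for a change score on arm and stratum. Keep change from baseline as description only, in line with item 1 of the same section.

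The cost is a few lines of wording and one degree of freedom. The baseline data are already planned, so nothing new is collected.
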